## **SAMPLE SIZE CALCULATION**

The unit of analysis will be set at the patient. In those patients with more than one implant fulfilling the inclusion criteria, a mean of the implants included will be taken into consideration for the analysis. Sample size was calculated according to the main outcome “complete disease resolution”. Taking into account that previous studies showed a disease resolution around 66.6% (de Tapia et al. 2019) after treatment by means OHI and mechanical debridement, we estimate that at least 50% of patients receiving OHI as a single therapy could present a complete resolution. Accepting an alpha risk of 5% and a beta risk of 10% in a two-sided test, 28 subjects are necessary. It has been anticipated a drop-out rate of 15%. In order to include a second group of patients receiving an usual management as control group, we will include a total of 56 patients (28 in each group).

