As mentioned before, the occurrence of PM is mainly influenced by plaque accumulation and therefore effective oral hygiene practices are fundamental in their prevention and management. In fact, there is evidence from experimental human studies that PM resolution may occur with adequate biofilm control (Meyer et al., 2017; Salvi et al., 2012; Schincaglia et al., 2017). The reversibility of experimental PM after the re-institution of plaque control has been confirmed by the decrease to baseline values of crevicular fluid levels of host-derived biomarkers (Salvi et al., 2012). And as it was stated in the latest expert consensus on the prevention and treatment of peri-implant diseases (Herrera et al., 2023), even though, the traditional treatment of PM includes mechanical professional cleaning, up to date the added benefit of professional mechanical/physical instrumentation as compared to OHI alone is not known.

It is therefore the aim of this randomized clinical trial to identify if there is any superiority of mechanical/physical instrumentation over OHI alone.

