## 3. Hypothesis

- The proper oral hygiene measures conducted by the patient after individualized OHI will achieve resolution of PM in a clinically relevant proportion of patients.
- The proper oral hygiene measures conducted by the patient after individualized OHI will reduce the expression of peri-implant pathogens as much as the combination of individualized OHI and professional mechanical debridement in a clinically relevant proportion of patients.
- The proper oral hygiene measures conducted by the patient after individualized OHI will reduce mBI as much as the combination of individualized OHI and professional mechanical debridement in a clinically relevant proportion of patients.
- The extent of inflammation measured as the mBI could be related with the degree of resolution of the disease according to the treatment.

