## **5. Results analysis**

The data contained in the CRFs will be entered into a database for data analysis and preparation of the final report.

The socio-demographic and clinical characteristics and other variables of interest of the patients included in the study will be described. Data will be presented as mean  $\pm$  SD; categorical data will be shown as percentage of positive patients.

The relationship between two qualitative variables will be calculated using the chi-squared test or Fisher's exact test (frequency  $< 5$ )

For ordinal variables, linear regression will be calculated using Kendall's tau coefficient.

Quantitative variables will be compared using the Student's t-test (< 2 categories), analysis of variance [ANOVA] (> 2 categories), linear regression test and Scheffé's multiple comparisons test or U Mann Whitney.

The linear relationship between the quantitative variables will be calculated using Pearson's correlation coefficient or Spearman's rank correlation test (when variable not normally distributed).

Changes *versus* baseline will be analyzed by Wilcoxon non-parametric test or Mc Nemar test.

A logistic regression model will be set in order to determine whether the initial extent of the inflammation, mBI, is related to disease resolution

Level of significance will be set at 0.05. The SPSS version 19.00 software (SPSS Inc., Chicago, IL, USA) will be used for all analyses.

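### 28 per group does not follow from the stated inputs: 66.6% vs 50% at two-sided 5% and beta 10% needs about 184 per group, and 28 gives about 24% power

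*Combined protocol and SAP*

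**What the plan says.** The Sample Size Calculation section (under 4. Material and methods) makes the patient the unit of analysis and sizes the trial on complete disease resolution. It takes a resolution rate of about 66.6% with OHI plus mechanical debridement from earlier work, and for OHI alone it says "we estimate that at least 50% of patients receiving OHI as a single therapy could present a complete resolution". It continues: "Accepting an alpha risk of 5% and a beta risk of 10% in a two-sided test, 28 subjects are necessary". It anticipates 15% drop-out. The last step is introduced by "In order to include a second group of patients receiving an usual management as control group", and the total becomes 56, with 28 in each arm. No test, null value, margin, formula or software is named, and the section does not say whether 28 allows for drop-out.

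Elsewhere, the Introduction gives the aim of the randomised trial as to "identify if there is any superiority of mechanical/physical instrumentation over OHI alone". One entry under 3. Hypothesis says instead that OHI "will reduce mBI as much as the combination of individualized OHI and professional mechanical debridement". For binary outcomes, 5. Results analysis states: "The relationship between two qualitative variables will be calculated using the chi-squared test or Fisher's exact test".

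**The concern.** Two rates 16.6 points apart and near the middle of the scale cannot be separated with 90% power by a few dozen patients. The number looked too small by a factor of six or more for the comparison the trial is randomised to make. The order of the text, with 28 first and a second group afterwards, suggests that a single-group figure was doubled.

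The stake is how the result will be read. If debridement really were better by the assumed 16.6 points, a trial of this size would most likely return a non-significant difference in resolution. Set beside a stated beta of 10% and a hypothesis that OHI does as well as the combination, that result could be taken as evidence that debridement adds nothing. The Introduction says this very question is unanswered.

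**Working it through.** **Inputs, all from Sample Size Calculation:** p1 = 0.666 (OHI plus debridement), p2 = 0.50 (OHI alone), two-sided alpha 0.05 (z = 1.96), beta 0.10 (z = 1.2816), drop-out 15%, 28 per group. The difference is 0.166 and the mean rate is 0.583.

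**1. Trying to reproduce 28 as a two-group comparison**

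Pooled formula: n per group = [1.96·√(2·0.583·0.417) + 1.2816·√(0.666·0.334 + 0.5·0.5)]² / 0.166² = (1.3667 + 0.8809)² / 0.02756 = 183.3, so **184**.

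- Unpooled variance: 180.1, so 181.
- Continuity-corrected: 195.2, so 196.
- Looser settings than the plan states still miss: one-sided 5% with 90% power needs 150, two-sided 5% with 80% power needs 138, and one-sided 5% with 80% power needs 109.

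**2. Trying to reproduce 28 as a one-group calculation**

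One-sample test: n = {[1.96·√(p0(1−p0)) + 1.2816·√(pA(1−pA))] / 0.166}².

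- Reference 66.6%, true 50%: 88.9, so 89. Power at 28 is 46%.
- Reference 50%, true 66.6%: 91.1, so 92. Power at 28 is 41%.

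Before-after McNemar test in the OHI group, from 0% resolved at baseline to 50% (discordant proportions 0.50 and 0): n = [1.96·√0.50 + 1.2816·√(0.50 − 0.25)]² / 0.50² = 16.4, so 17. An exact calculation also gives 17. With drop-out, 17/0.85 = 20.

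**3. Trying non-inferiority**

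The plan gives no margin, so any margin is an assumption. With both true rates at 66.6%, one-sided 2.5% and 90% power, n = (1.96 + 1.2816)²·2·0.666·0.334 / margin². A 40-point margin needs 30 per group and a 45-point margin needs 24, so 28 would imply a margin above 40 points.

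None of these gives 28.

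**4. Drop-out**

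If 28 evaluable patients are needed, 28/0.85 = 32.9, so 33 per group must be enrolled. If 28 are enrolled, 28 × 0.85 = 23.8, so about 24 are evaluable.

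**5. What 24 to 28 evaluable patients per group provide**

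Approximate power = Φ{[0.166·√n − 1.3667] / √(0.666·0.334 + 0.25)}. At n = 28 this is Φ(−0.710) = 0.239, and at n = 24 it is Φ(−0.805) = 0.210. The exact figures come from enumerating both binomials.

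| | 28 per group | 24 per group |
|---|---|---|
| Power, normal approximation | 23.9% | 21.0% |
| Power, exact chi-squared | 23.3% | 23.1% |
| Power, Fisher | 16.2% | 15.0% |
| Difference detectable with 90% power, 66.6% fixed | 41.6 points | 44.5 points |
| Difference detectable with 90% power, 50% fixed | 38.5 points | 40.9 points |
| Expected 95% CI half-width | 25.5 points | 27.5 points |

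The half-width is 1.96·√[(0.666·0.334 + 0.25)/n]. Centred on 16.6 points, the interval would run from about −9 to +42 points (28 per group) or −11 to +44 points (24 per group).

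**The case against.** The best defence is that the section never says 28 powers a between-group test. It reaches 28 first and adds the control group afterwards. The first entry under 3. Hypothesis concerns OHI alone achieving resolution in a worthwhile share of patients, and McNemar's test is listed for changes from baseline. Other common McNemar forms for 0% to 50% give 20.2, 21.0 and 24.9 before drop-out. With the form used above, the drop-out-inflated figures run from 20 to about 30, so 28 lies inside the range of a plausible before-after calculation. With 24 evaluable patients, that test has over 99% exact power.

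This stands as a possible origin of the number, but no form tried gives 28 exactly and the plan names none of them. More importantly, a before-after calculation in one arm says nothing about the difference between arms, which is the subject of both the Introduction's aim and the primary objective.

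Three further points are fair.

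- The low power applies to binary resolution. The primary objective speaks of mBI reduction, and power for that as a quantitative outcome cannot be computed because no standard deviation is given. Resolution is nevertheless the outcome the plan itself chose for sizing.
- The 50% is described as a floor. A true OHI rate between 50% and 66.6% narrows the difference and lowers power further, so this does not help.
- Nothing in the plan says a non-significant result will be read as equivalence. That risk is inferred from the hypothesis wording.

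**Conclusion.** The concern holds. The stated rates, alpha and beta require about 184 evaluable patients per group (181 to 196 by formula) for the randomised comparison of complete resolution. The planned 28 per group gives about 24% power, and the 24 left after drop-out about 21% (15–16% with Fisher's test). The true beta at the assumed rates is therefore about 76–79%, or 84–85% with Fisher's test, against the stated 10%. No one-sample, before-after or two-group calculation tried on the stated inputs yields 28, so the comparative aim has no valid power statement. These figures rest only on the plan's own rates and error levels, one binary outcome per patient, and equal groups. The before-after figure also assumes that no patient is resolved at baseline.

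**What to change.** Rewrite the sample-size paragraph without changing enrolment:

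1. Remove the claim that 28 subjects give a beta of 10% at 66.6% versus 50%.
2. State which comparison, which hypothesis (the superiority aim or the as-good-as hypothesis) and which formula 28 comes from, and whether it is the enrolled or the evaluable number.
3. State that 24–28 evaluable patients per group give about 21–24% power for 66.6% versus 50% (about 15–16% with Fisher's test). State also that 90% power is reached only for a difference of about 42–45 points with 66.6% fixed, or 39–41 points with 50% fixed.
4. Give the expected 95% confidence-interval half-width for the between-group difference, about 25–28 percentage points. State that a non-significant result will not be taken as evidence that debridement adds nothing.

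The cost is one paragraph and a much less favourable stated power. No patients, visits or data are added.

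### The plan does not show whether 28 per group is before or after the 15% drop-out allowance; either way about 24 per group are expected to be evaluable, a number it never states

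*Combined protocol and SAP*

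**What the plan says.** All the figures stand in one paragraph, under Sample Size Calculation in section 4 of the combined protocol and SAP.

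- The expected resolution rates are 66.6% with oral hygiene instruction plus debridement ("previous studies showed a disease resolution around 66.6" per cent) and 50% with instruction alone.
- The number is tied to the error rates: "Accepting an alpha risk of 5% and a beta risk of 10% in a two-sided test, 28 subjects are necessary".
- The drop-out rate follows directly: "28 subjects are necessary. It has been anticipated a drop-out rate of 15" per cent.
- The enrolment is then given: "we will include a total of 56 patients (28 in each group"). The only reason offered for going from 28 to 56 is the addition of a control group.

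The plan prints no pair of numbers before and after drop-out, and no later section adds an allowance. Section 5 (Results analysis) defines no analysis set and no rule for missing outcomes.

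**The concern.** The number called necessary and the number enrolled per group are the same, although a 15% loss is expected between enrolment and analysis. One number cannot be both the evaluable requirement and the enrolment target unless nobody drops out. The plan should say which it is.

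This paragraph is the trial's only justification of its size. As it stands, a reader cannot tell how many evaluable patients were planned. If 20 per group complete, the shortfall is 8 against a target of 28 and 4 against a target of 24, and the plan does not say which applies. Any power or precision statement attached to 28 evaluable patients would also be somewhat too favourable.

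**Working it through.** **Inputs**, all from Sample Size Calculation: two-sided alpha 5%; beta 10%; rates 0.666 and 0.50; drop-out 15%; 28 enrolled per group; the patient as unit of analysis.

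**1. The plan's own figure.** For two independent proportions with a pooled variance under the null,

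n = [1.960 × √(2 × 0.583 × 0.417) + 1.282 × √(0.666 × 0.334 + 0.5 × 0.5)]² / 0.166² = (1.367 + 0.881)² / 0.0276 ≈ 183.3, so 184 per group.

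With a continuity correction it is 196, and with unpooled variance 181. The text reaches 28 before it adds the control group, so a single-group test of 50% against a fixed 66.6% was also tried: 89 (two-sided, 90% power), falling to 52 (one-sided, 80% power). None of these gives 28, or the 23 to 24 that would become 28 after an allowance. The figure is not reproduced, so recomputation cannot show whether 28 includes drop-out.

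**2. If 28 is before drop-out.** Enrolment needed = 28/(1 − 0.15) = 32.9, so 33 per group (66 in total). The plan is then 5 per group short.

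**3. If 28 is after drop-out.** Working back, 23/0.85 = 27.1, which rounds up to 28; with the cruder multiplier, 24 × 1.15 = 27.6, also 28. The number needed for analysis would be about 23 to 24.

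**4. Expected evaluable patients, on either reading.** 28 × 0.85 = 23.8 per group; 56 × 0.85 = 47.6. That is about 24 per group, 48 in all, if patients who drop out are not analysed.

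**5. Power and precision.** Power = Φ{[0.166 × √n − 1.367] / 0.687}, where 1.367 is the first term in step 1 and 0.687 = √(0.666 × 0.334 + 0.5 × 0.5). The half-width of the 95% confidence interval for the difference is 1.96 × √[(0.666 × 0.334 + 0.5 × 0.5)/n].

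| Evaluable per group | Power | Half-width (percentage points) |
|---|---|---|
| 24 | 21% | 27.5 |
| 28 | 24% | 25.5 |

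Enrolling 33 per group would leave 33 × 0.85 = 28.05 evaluable, which is the second row. Even 33 evaluable per group would give only about 27% power.

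**The case against.** The strongest reply is that 28 may already be the recruitment number. The drop-out sentence comes straight after it and before the enrolment sentence, so it can be read as one more input. Step 3 shows that the arithmetic allows this. On that reading the three printed figures agree, and about 24 evaluable per group is simply what was planned.

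This stands, and it rules out two stronger readings. A reader might infer that the allowance was never applied, or that the printed figures contradict each other however they are read. The documents establish neither, because they do not say that *necessary* means evaluable. Nor does recomputation settle it. Comparisons using a rate that the plan does not give can produce 23, and so 28 after the allowance (50% against 5% with a continuity correction is one), but nothing in the text points to such a rate.

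Three further replies have some force:

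- The effect of drop-out is small, about 3 points of power and 2 points of half-width. That is correct.
- The plan promises no confidence interval, so the half-width is illustrative. Also correct.
- The larger defect is that 28 does not follow from the stated inputs. Also correct, and it is the reason to make both corrections together. It does not remove the need to state the evaluable number.

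**Conclusion.** The point holds as a failure to disclose, with an unapplied allowance as one of two possible explanations. The literal order of the text favours the before-drop-out reading (33 per group needed, 28 enrolled) but does not prove it. On the other reading the requirement of about 23 to 24 is missing from the plan. On both, about 24 per group are expected to be evaluable, and that number appears nowhere.

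A reader might attribute the whole gap between 90% and about 21% power to drop-out. That would be wrong: 28 evaluable per group would already give only about 24%, and drop-out accounts for the remaining 3 points.

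The conclusion assumes that losses are 15% in each group and that drop-outs are left out of the analysis. The power figures assume a two-sided comparison of two independent proportions at the plan's rates.

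**What to change.** Do not enrol more patients on account of this point. Going to 33 per group would raise power only from about 21% to 24%, nowhere near 90%. Instead, rewrite the end of Sample Size Calculation so that it:

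1. states that 56 patients (28 per group) will be randomised and that, with 15% drop-out, about 24 per group are expected to be evaluable;
2. says whether 28 is before or after the 15%, and if after, gives the number before the allowance;
3. restates power, or the expected precision of the difference, at 24 per group, in the same revision that corrects the 28 itself.

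The cost is a corrected sample size statement, with no change to recruitment, procedures or visits. It is more than a cosmetic edit, because the stated 90% power cannot be kept: at the plan's own rates the figure would be about 21%, with a half-width of about 27.5 percentage points.

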## **CALIBRATION**

The examiners ([name] and [name]) will follow a calibration exercise by evaluating peri-implant soft tissue parameters (PPDi and mBI) in 5 patients with PM, in two subsequent visits, 48 hours apart. The intra-examiner reproducibility will be accepted when a minimum intra-class correlation coefficients of 0.80 is achieved.

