### **Clinical, radiographic and microbiological examination**

At baseline, 1 (1m) and 3 months (3m) after treatment, two calibrated examiners ([name] and [name]) will record the following clinical variables using an electronic, pressure-calibrated probe (PA\_ON Probe, Orange Dental®, [name], Biberach, Germany), with a standardized probing force of 0.20 N.

At the full-mouth level, the following parameters will be evaluated:

- (1) Full mouth plaque Index (FMPI), assessed dichotomously at four sites per tooth (mesial, buccal, distal, and lingual).
- (2) Full mouth bleeding index (FMBI), assessed dichotomously as presence or absence of bleeding after 30 seconds of gently probing (Ainamo and Bay, 1975).
- (3) Full mouth probing pocket depth (FMPPD), measured at six sites around each tooth, except third molars.

At local level, in six sites around each implant, the following clinical variables will be recorded:

- (1) Modified plaque index (mPI) (Mombelli et al., 1987)
- (2) Modified bleeding index (mBI) (Mombelli et al., 1987), dichotomized in presence/absence of bleeding and selected as the primary outcome (BOP).
- (3) Suppuration on probing (SOP), assessed dichotomously as presence or absence of suppuration within 30 seconds after probing.
- (4) Implant probing pocket depth (PPDi), measured from the mucosal margin to the bottom of the probable pocket.
- (5) Implant mucosal recession (MRI), measured from the implant neck to the mucosal margin.

Disease resolution will be considered when a mBI <0.16 is achieved, as it was established in the last consensus performed to develop the clinical practice guidelines on the treatment of peri-implant diseases (Herrera et al. 2023).

Individual acrylic resin occlusal stents, exhibiting six vertical grooves per implant (mesiobuccal, midbuccal, distobuccal, mesiolingual, midlingual and distolingual), will be built in order to allow a reproducible direction and angulation during probing.

A periapical radiograph of all implants involved in the study will be taken using a paralleling cone technique and a film-holder (7mA- 60kV/20ms) at baseline and at 3 months after treatment, in order to detect any loss of supporting bone.

Furthermore, sampling for microbiological test will be conducted at baseline, 1m and 3months after treatment.

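### Two examiners score the primary bleeding outcome, but calibration tests each only against themselves, so a systematic difference between them would pass unseen

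*Combined protocol and SAP*

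**What the plan says.** The Clinical, radiographic and microbiological examination section assigns the clinical measurements to two people: "At baseline, 1 (1m) and 3 months (3m) after treatment, two calibrated examiners" record them. Among these is mBI at six sites per implant, "dichotomized in presence/absence of bleeding and selected as the primary outcome (BOP". The same section sets the patient-level endpoint: "Disease resolution will be considered when a mBI <0.16 is achieved". The Sample size calculation section takes the patient as the unit and averages over eligible implants.

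The Calibration section has the examiners score PPDi and mBI "in 5 patients with PM, in two subsequent visits, 48 hours apart". The only acceptance rule is "The intra-examiner reproducibility will be accepted when a minimum intra-class correlation coefficients of 0.80 is achieved".

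The protocol sets no between-examiner criterion and no agreement measure for bleeding as present or absent. It does not say how patients or visits are divided between the examiners, and the Study design section does not stratify randomisation by examiner. The Results analysis section does not mention examiner.

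Three features do standardise measurement: an electronic probe "with a standardized probing force of 0.20 N", individual grooved stents "in order to allow a reproducible direction and angulation during probing", and a step-by-step procedures guidebook (Examinations section).

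**The concern.** An intra-examiner ICC asks whether an examiner repeats his or her own readings. A constant difference in what two examiners call bleeding largely escapes it, because each can be consistent around a different threshold. The endpoint is sensitive to such a difference: resolution in a one-implant patient requires every one of six sites to be read as non-bleeding.

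There are two routes to bias. If one examiner sees more patients in one arm, the threshold difference enters the between-arm comparison of resolution. If a patient is scored by one examiner at baseline and the other at follow-up, it enters the Wilcoxon and McNemar tests of change. Without either link, the cost is extra misclassification.

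**Working it through.** The 0.80 threshold is a chosen limit, so there is no plan figure to reproduce. The checks below ask whether the rule can accept a discordant pair, and how much that could matter.

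**Inputs from the protocol.** Two examiners; six sites per implant; resolution if mBI <0.16; 5 calibration patients with two readings; 28 patients per arm; assumed resolution of 66.6% (OHI plus debridement) and 50% (OHI alone), a difference of 16.6 points.

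**Assumptions (not in the protocol).** Dichotomised scoring and independent sites. Examiner A over-calls bleeding at 2% of healthy sites and examiner B at 5%. A second model, with different assumptions, gives a range.

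**1. Can a discordant pair pass?** Simulated examiners scored a four-level index from the same latent inflammation (SD 1), with repeat error SD 0.3 and B's threshold shifted by 0.5. The intra-examiner ICCs were 0.84 and 0.82, so both pass. The between-examiner absolute-agreement ICC was 0.72 and kappa for bleeding 0.59, with 50% and 32% of sites read as bleeding. With repeat error SD 0.2 and a shift of 0.8, the intra-examiner ICCs were 0.89 and 0.87, the between-examiner ICC 0.60 and kappa 0.43.

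**2. How sensitive is resolution to single sites?** The table gives the probability that a truly resolved patient is classed as resolved.

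| Implants | Sites allowed to bleed | A (2%) | B (5%) | Gap |
|---|---|---|---|---|
| 1 | 0 of 6 (1/6 = 0.167 fails) | 0.98^6 = 88.6% | 0.95^6 = 73.5% | 15.1 points |
| 2 | 1 of 12 (1/12 = 0.083 passes) | 97.7% | 88.2% | 9.5 points |
| 3 | 2 of 18 (3/18 = 0.167 fails) | 99.5% | 94.2% | 5.3 points |

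The last two rows are binomial probabilities of at most 1 of 12 and at most 2 of 18.

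**3. How much reaches the between-arm comparison (one implant)?** Over-calling changes the result only for truly resolved patients, so false difference = gap × true resolution rate × difference between arms in examiner B's share.

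- Full confounding (share difference 1): 15.1 × 0.50 = 7.5 points; 15.1 × 0.666 = 10.0 points.
- 70/30 split (share difference 0.4): 0.4 × 7.5 = 3.0; 0.4 × 10.0 = 4.0 points.
- Chance imbalance, each patient equally likely to see either examiner: SD of the share difference = √(2 × 0.25/28) = 0.134; 1.96 × 0.134 = 0.26; 0.26 × 7.5 to 0.26 × 10.0 = about 2.0 to 2.6 points.
- Sampling standard error of the arm difference, for comparison: √(0.666 × 0.334/28 + 0.5 × 0.5/28) = 0.130, or 13 points.
- Balanced examiners: no bias. If 16.6 points is the true difference, A alone would see 16.6 × 0.886 = 14.7, B alone 16.6 × 0.735 = 12.2, and an even mix about 13.5.

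**4. Range under the second model.** Here resolution is 0 of 6 sites bleeding, patient and site SD are 1 each, repeat error SD is 0.3, and examiner A reads 66.6% and 50%.

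| Threshold shift | 0.3 | 0.5 | 0.8 |
|---|---|---|---|
| Arm difference, examiners balanced | 15.9 | 15.2 | 14.1 |
| False difference, 70/30, both arms at 66.6% | 3.4 | 5.3 | 7.8 |
| False difference, full confounding, both arms at 66.6% | 8.4 | 13.3 | 19.5 |

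**5. How precise is the existing check?** For an observed ICC of 0.80 with two readings, F = (1 + 0.8)/(1 − 0.8) = 9. With one value per patient and 5 patients, the one-way 95% interval is about 0.10 to 0.98. With 30 site values (5 × 6) and clustering ignored, it is about 0.62 to 0.90. The Calibration section does not name the unit.

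**The case against.** The strongest reply is that the plan already controls much of what makes examiners differ: force, direction and angulation of probing, and procedure. Allocation is randomised, so an examiner imbalance arising by chance is random error, and step 3 puts it at 2.0 to 2.6 points against a standard error of 13. The ICC is also a reasonable index for PPDi and for mBI on its full scale. All of this stands. The standardisation reduces examiner differences but does not test whether two people read bleeding alike, and randomising patients to arms does not govern who examines them.

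A reader might infer more: that because a 15-point examiner gap is about the size of the 16.6-point treatment difference, the result could be overturned. The documents do not support that. The 15 points describe two examiners classing the same truly resolved one-implant patients, whereas the 16.6 points are a difference between arms. The over-call rates are assumed, and the gap shrinks as more implants are averaged. The protocol is silent on how examiners are allocated; it does not show a link with arm.

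The small calibration sample also limits the remedy. With 30 sites, 2% versus 5% means 0.03 × 30 = 0.9 extra calls even if every site were healthy, and these patients have mucositis. Agreement in 5 patients can reveal only large differences, such as 50% versus 32% of sites bleeding (0.18 × 30 = 5.4 sites).

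**Conclusion.** The point holds in conditional form. Followed exactly, the stated rule would accept two self-consistent examiners who read bleeding differently, and nothing else in the plan would detect it. With examiners balanced across arms, the consequence is mainly noise and mild attenuation. Bias requires examiner to be related to arm, or to visit within a patient for the change tests; the plan neither shows nor prevents this.

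Under assumed over-call rates of 2% and 5% and one implant, the false between-arm difference is about 3 to 4 points at a 70/30 split and 7.5 to 10 under full confounding. The threshold-shift model, at its 66.6% anchor, widens these to about 3 to 8 and 8 to 20 points. All of these are illustrations, since the protocol gives no examiner error rates. The change is worth making because it is cheap and because examiner identity, if not recorded at the visit, may be impossible to recover later.

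**What to change.** In the Calibration section, state that both examiners score the same 5 patients at the two visits already planned. Add a between-examiner criterion with a stated limit: kappa together with raw agreement for site-level bleeding yes/no, and an absolute-agreement ICC for PPDi. Recalibrate if the limit is missed. Name the unit of each statistic, and acknowledge that 5 patients can detect only large differences.

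In the examination section, keep each patient with one examiner at baseline, 1 and 3 months, which protects the change tests. Spread the two examiners evenly across arms, which protects the comparison of resolution. Record the examiner in the CRF at every visit.

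In the Results analysis section, add a sensitivity analysis of the between-arm resolution comparison, stratified by or adjusted for examiner. Adding examiner only to the planned logistic model would not clearly do this, because that model is described as relating baseline mBI to resolution, not as comparing arms.

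The cost is a few sentences, agreement statistics from the planned calibration sessions, a slight constraint on appointments and one extra analysis.
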